## 10 STUDY OVERSIGHT

NIDCR's Medical Monitor reviewed this clinical trial based upon the trial study design described in the grant application and the non-significant risk (NSR) letter from the FDA that was provided by [name] to NIDCR. In addition to the PI's responsibility for oversight, it has been determined that the trial will be overseen via Medical Monitor Oversight Reporting (MMOR). The MMOR will be requested at 6-month intervals during the data collection phase of the trial. NIDCR's program officer, [name], will provide more information about timelines for reporting after the clinical trial is activated.

## **11 CLINICAL SITE MONITORING**

Clinical site monitoring will not be conducted for this trial. The NIDCR reserves the right to conduct independent audits as necessary.

Quality and integrity of study data and data collection methods will primarily involve quality management (QM) procedures to ensure adherence to human subject protections, including completeness of consenting procedures, and completeness and accuracy of data collection. These QM procedures are detailed in the protocol, Sections 14 and 16, as well as the Manual of Procedures (MOP).

## 12 STATISTICAL CONSIDERATIONS

### 12.1 Study Hypotheses

The risk of developing TMD pain in patients undergoing 3rd molars removal in the EC group will be statistically lower within the 6-month follow-up interval than in the UC group.

### 12.2 Sample Size Considerations

This study's sample size is based on the incidence of TMD pain following 3rd molar removal reported by Huang et al. That observational study reported that among patients undergoing 3rd molar removal, the incidence of jaw joint symptoms lasting more than 1 month was 34.3 per 100 person-years. Among those who did not have a 3rd molar extraction, the rate was 8.8, for a relative risk of 3.8. The incidence of TMD pain reported by patients undergoing surgery was over 30%.

**Primary analysis.** We present a conservative power calculation that assumes we have a single binary outcome (TMD pain yes vs. no) instead of the three measures per person we will collect. The calculations shown below assume two-sided tests and a false positive rate of 5% (alpha = 0.05).

Table 1 shows that 132 patients per group gives 80% power to detect a conservative relative risk of 2.0. To estimate this, we considered a TMD pain incidence of 14% and alpha (type I error) 5%. Table 1's incidences and relative risks are based on data from Huang et al. Note that Huang et al. reported TMD pain incidence over 30%; the current study will have adequate power if the control group's TMD pain incidence is much lower. We will randomize 294 subjects into the study. Assuming 10% loss to follow-up (90% retention), the total sample size will be 264 (132 per group). The assumed retention of 90% is a conservative estimate based on [name] experience in his previous RCT, where 98 of 106 (92%) TMD participants completed their 5-year follow-up visit. Therefore, we anticipate, with patient incentives, that we will obtain 90% or more retention at the 6-month follow-up.

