Over 10 million 3rd molars (wisdom teeth) are extracted from about 5 million people in America each year.(1) More than 11 million patient days of “standard discomfort or disability” – pain, swelling, bruising and malaise – result postoperatively.(1) Although the American Association of Oral and Maxillofacial Surgeons guidelines state that consent forms for 3rd molar extractions should include injury to the temporomandibular joint (TMJ) or associated muscles(17), there are few reports of the trauma to the TMJ or jaw muscles from this procedure.(1) One of the best studies assessing development of TMD after 3rd molar extractions is a large prospective cohort study of young adults.(3) Huang et al. assessed the onset of jaw joint symptoms (i.e., TMJ noise and jaw pain) in individuals who had 3rd molar extractions compared to those who did not. Of the 517 participants with follow-up data, 39% (n = 201) had a total of 720 3rd molars extracted, with 68% reporting that 'intravenous sedation' or general anesthesia was used. Among patients undergoing 3rd molar removal, the rate of TMD lasting more than 1 month was 34.3 per 100 person-years compared to 8.8 among those who did not have 3rd molar extractions. The relative risk of developing TMD was 3.8 and the rate of TMD reported by patients undergoing this surgery was greater than 30%. This study's findings are limited by its low follow-up rate (40 to 50% for follow-up questionnaires at different intervals). Further, a retrospective study reported that almost a quarter of new onset TMD cases in young adults were associated with 3rd molar removal.(2) In a cross-sectional study of patients aged 18.7 + 1.1 years, the occurrence of 3rd molar extractions was significantly associated with TMD ( $P<0.001$ ). (7) Finally, in an age and sex matched case-control study, at 6 months follow-up, patients who had 3rd molar extractions had significantly more TMJ and jaw muscle pain than controls who did not have this surgery ( $P<0.05$ ). (6) These findings suggest removing 3rd molars is associated with development of TMD and that this patient safety issue is not addressed by current methods to protect the jaw during this surgery. Providing better support for

the jaw during 3rd molar extractions to prevent hyperextension and excessive force on the jaw would be expected to alleviate the physical stress on the jaw and reduce patient suffering and jaw injury. (18, 19)

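### The 80% power in section 12.2 needs a usual-care risk of 28% in six months, so the assurance that power stays adequate well below 30% is wrong at a relative risk of 2.0

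*Combined protocol and SAP*

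**What the plan says.** Section 12.2 sets the test: "The calculations shown below assume two-sided tests and a false positive rate of 5% (alpha = 0.05". It then states: "Table 1 shows that 132 patients per group gives 80% power to detect a conservative relative risk of 2.0". The planning value follows: "we considered a TMD pain incidence of 14% and alpha (type I error) 5" (per cent). Neither the sentence nor Table 1 says which arm has the 14%.

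The planning values are attributed to one observational cohort, for which the section gives two figures. The first is a person-time rate: "the incidence of jaw joint symptoms lasting more than 1 month was 34.3 per 100 person-years". The second is a percentage with no period attached: "The incidence of TMD pain reported by patients undergoing surgery was over 30" (per cent). Section 2.1 describes what that cohort measured: it "assessed the onset of jaw joint symptoms (i.e., TMJ noise and jaw pain").

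Section 12.2 then uses the over-30% figure as a margin, saying that power remains adequate with a control-group incidence far below it.

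The trial's own outcome is different. Section 3.2.1 defines a binary outcome within six months, built from two pain items, with no noise item and no minimum duration. The hypothesis in section 12.1 is that the EC risk will be "statistically lower within the 6-month follow-up interval than in the UC group".

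**The concern.** The 80% figure can be judged only if the reader knows the control risk it assumes. The one incidence quoted is 14%, and the next remark concerns the control group, so it is natural to take 14% as the control risk and 30% as a comfortable upper value. If 14% is in fact the EC risk, the control risk is 28% and almost no margin remains below 30%.

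The support for 28% then matters. Neither source figure is a six-month risk of pain. One is a rate per person-year for symptoms that include noise and last more than a month; the other has no time horizon. The plan converts neither. If the true UC risk is well below 28%, the trial has materially less than 80% power at RR 2.0, and a null result would be read against a power claim the design does not have.

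**Working it through.** **Inputs.** Two-sided alpha 0.05, 80% power, 132 per group, RR 2.0, incidence 14% and 10% loss (section 12.2); 1:1 allocation (section 5.4.1); 34.3 per 100 person-years (sections 2.1 and 12.2); six-month binary outcome (section 3.2.1). The calculation follows the plan's own simplification to one binary outcome per patient.

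**Formula.** Pooled-variance comparison of two proportions, with p the mean of p1 and p2:

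n = [1.96·√(2p(1−p)) + 0.8416·√(p1(1−p1) + p2(1−p2))]² / (p1 − p2)²

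**Step 1: reproduce 132.**
- 28% vs 14%: p = 0.21, 2p(1−p) = 0.3318, and the sum of variances is 0.3220. n = (1.1290 + 0.4776)² / 0.14² = 131.7, so 132. This matches.
- 14% vs 7%: n = 299.9, so 300. Other forms do not recover 132 either: 298 unpooled, 328 with continuity correction, 237 one-sided.
- With the listed incidence as the lower arm, all 12 cells of Table 1 reproduce to within one patient.
- Loss: 264/0.90 = 293.3, which agrees with 294 randomized.

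The lowest UC risk anywhere in Table 1 is therefore 2.0 × 14% = 28%. The table contains no case with a control risk below that.

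**Step 2: power at 132 per group, RR 2.0.**

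| UC risk | EC risk | Power |
|---|---|---|
| 30% | 15% | 83.5% |
| 28% | 14% | 80.1% |
| 25% | 12.5% | 74.2% |
| 20% | 10% | 62.5% |
| 15.8% | 7.9% | 50.9% |
| 14% | 7% | 45.8% |
| 10% | 5% | 33.7% |

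Apart from the 15.8% row, this table uses nothing from the cited cohort. It is enough to show that the assurance fails at RR 2.0.

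**Step 3: put the quoted rate on a six-month basis (assumption: constant hazard).**
- Risk = 1 − exp(−0.343 × 0.5) = 15.8%. Simple halving gives 17.2%.
- Power at UC 15.8%: 51% at RR 2.0 (51.4% by exact enumeration of the chi-squared test), 69% at RR 2.5 and 80% at RR 3.0. At UC 17.2% and RR 2.0 it is 55%.
- 80% power at UC 15.8% and RR 2.0 would need 263 per group.
- A constant hazard giving 28% in six months is −ln(0.72)/0.5 = 65.7 per 100 person-years, 1.9 times the quoted rate.

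**Step 4: relax the constant hazard.**
- If 75% of a year's cumulative hazard fell in the first six months: risk 1 − exp(−0.343 × 0.75) = 22.7%, power 69% at RR 2.0.
- If all of it did: risk 1 − exp(−0.343) = 29.0%, power 82%.

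**The case against.** The strongest reply is that nothing is miscalculated. The 132 is right for 28% vs 14%, Table 1 reproduces, and the loss adjustment is right. That stands: the fault is in what the text says about the figures.

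A reader might infer that the over-30% figure is simply the 34.3 rate renamed as a percentage of patients with pain. The documents do not settle this. Both sections give the two figures in separate sentences, and the percentage could be a separate cumulative proportion, even one for pain alone. What can be said is that it has no time horizon.

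A reader might also infer that the trial's real power is 51%. That needs a constant hazard, a weak default for symptoms that follow a one-day operation; Step 4 shows that early onset could bring the risk back to about 29%. The endpoint differs in both directions: leaving out noise lowers the trial's risk, while having no minimum duration, with a first questionnaire at about 30 days, raises it. The documents give no share of noise-only cases, so neither effect can be sized. The 51% is also specific to RR 2.0, and the planned analysis by generalized estimating equations over three visits is a different analysis, whose power cannot be computed from the documents.

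These points limit the 16% and 51% to a scenario. They do not touch Steps 1 and 2, which need neither the cohort nor any hazard assumption.

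**Conclusion.** Section 12.2 is wrong as written on one point and unsupported on another.

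- **Wrong at RR 2.0:** the assurance about a control incidence well below 30%. On the only reading that reproduces 132, the stated 80% is met at a UC risk of 28% and lost just below it, about two percentage points under the quoted 30%. Power is 74% at 25%, 62.5% at 20% and 46% at 14%. This rests only on the plan's own single-outcome simplification.
- **Unsupported:** a six-month UC pain risk near 28%. The only time-anchored figure in the documents is a person-year rate of noise and pain symptoms that is never converted. At constant hazard it gives about 16% and about 51% power at RR 2.0; with earlier onset the same rate is compatible with up to about 29% and 82%.

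The documents do not show that Table 1 is miscalculated, that 51% is the trial's power, or that the sample size must rise.

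**What to change.** In section 12.2:

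1. State that 14% is the assumed EC risk and 28% the assumed UC risk, and label the incidence column of Table 1 as the EC arm.
2. Give each cohort figure with its time base and endpoint: 34.3 per 100 person-years for noise and pain symptoms lasting more than one month, and the period and endpoint behind the over-30% figure, or a statement that these are unknown.
3. Add the six-month conversion of the rate (about 16%) with its constant-hazard assumption, and say in which direction early onset, the absence of a minimum duration and the exclusion of noise would move it.
4. Tabulate power at 132 per group for UC risks from 10% to 30% at RR 2.0, as in Step 2.
5. Delete the sentence that offers the over-30% figure as a margin, or correct it to say that at RR 2.0 power falls below 80% once the UC risk is under 28%.

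The sample size stays at 294 randomized. The work is a rewording of one section and one added table; the cost is a less favourable power statement.

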**Table 1. Sample size per group**

TMD pain incidence	Relative risk		
	2.0	2.5	3.0
14%	132	65	39
20%	81	38	22
25%	58	26	14
30%	42	18	9

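### Section 12.2's 132 per group assumes 28% TMD pain in Usual Care, not 14%, so at the design relative risk of 2.0 power is not adequate when control incidence is much below 30%

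*Combined protocol and SAP*

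**What the plan says.** Section 12.2 treats the outcome as one binary result per patient, with a two-sided alpha of 0.05. It states that "Table 1 shows that 132 patients per group gives 80% power to detect a conservative relative risk of 2.0", and that the incidence used was 14%. It does not say whether 14% applies to UC or EC. Table 1 lists sizes per group for incidences of 14%, 20%, 25% and 30% and relative risks of 2.0, 2.5 and 3.0; its first column names no arm either.

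The section then recalls that the cited cohort study reported an incidence over 30% and concludes that "the current study will have adequate power if the control group's TMD pain incidence is much lower". No relative risk is attached to that statement. Allowing for 10% loss to follow-up, 294 patients are randomized to leave 264.

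Section 12.1 fixes the direction of the effect: risk in the EC group "will be statistically lower within the 6-month follow-up interval than in the UC group".

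**The concern.** The sentence about a much lower control incidence follows only if 14% is the control-arm figure, since 14% would then lie far below 30%. If 14% is the device-arm figure, a relative risk of 2.0 puts UC at 28%, just under the cited value, and little room is left.

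This is the trial's only sample-size justification. If the arm is misread, a reader will believe the trial has 80% power to detect 14% against 7%. A null result at a UC incidence of, say, 20% could then be taken as coming from an adequately powered trial.

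**Working it through.** **Inputs.** From Section 12.2: two-sided alpha 0.05, power 80%, 132 per group, relative risk (RR) 2.0, listed incidence 14%, and the 12 cells of Table 1. Section 5.4.1 gives equal allocation. Section 12.1 makes EC the lower-risk arm.

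**Formula.** Pooled-variance comparison of two proportions, with p̄ = (p1 + p2)/2:

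n = [1.960·√(2p̄(1−p̄)) + 0.842·√(p1(1−p1) + p2(1−p2))]² / (p1 − p2)²

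**Step 1: reproduce the stated 132.**

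- 14% as the lower-risk arm (28% vs 14%, p̄ = 0.21): (1.1290 + 0.4776)² / 0.14² = 131.7, which rounds to 132.
- 14% as the higher-risk arm (14% vs 7%, p̄ = 0.105): (0.8497 + 0.3625)² / 0.07² = 299.9, so 300.

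**Step 2: repeat for all of Table 1.** Each entry gives RR 2.0 / 2.5 / 3.0.

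| Listed incidence | Printed | Listed value is the lower-risk arm | Listed value is the control arm |
|---|---|---|---|
| 14% | 132 / 65 / 39 | 131.7 / 64.7 / 39.2 | 299.9 / 195.5 / 151.3 |
| 20% | 81 / 38 / 22 | 81.2 / 38.5 / 22.3 | 199.0 / 130.1 / 100.8 |
| 25% | 58 / 26 / 14 | 57.7 / 26.3 / 14.5 | 151.9 / 99.5 / 77.3 |
| 30% | 42 / 18 / 9 | 42.0 / 18.1 / 9.2 | 120.5 / 79.2 / 61.6 |

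All 12 cells match to rounding under the first reading and none under the second. Continuity-corrected, unpooled, arcsine and one-sided variants do not rescue the second reading either: for 14% vs 7% they give 328, 298, 293 and 237.

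The 132 therefore rests on UC 28% vs EC 14%. The lowest UC incidence implied anywhere in Table 1 is 14% × 2.0 = 28%, and the 30% row implies UC of 60%, 75% and 90%. The table contains no scenario with a control incidence much below 30%.

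**Step 3: power at 132 per group, by UC incidence.**

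Power = Φ{ [|p1 − p2|·√132 − 1.960·√(2p̄(1−p̄))] / √(p1(1−p1) + p2(1−p2)) }

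For UC 25% vs EC 12.5%: (1.4361 − 1.0819)/0.5449 = 0.650, so power is 74.2%. For UC 20% vs EC 10%: (1.1489 − 0.9897)/0.5000 = 0.318, so power is 62.5%.

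| UC incidence | RR 2.0 | RR 2.5 | RR 3.0 |
|---|---|---|---|
| 35% | 90% | 98% | >99% |
| 30% | 83.5% | 95% | 98.5% |
| 28% | 80% | 93.5% | 98% |
| 25% | 74% | 90% | 96% |
| 20% | 62.5% | 81% | 89.5% |
| 16% | 52% | 70% | 80.5% |
| 14% | 46% | 63% | 74% |

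Exact enumeration of the pooled z test at RR 2.0 agrees: 84.1% at UC 30%, 80.7% at 28%, 74.9% at 25%, 62.9% at 20% and 46.5% at 14%.

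**Step 4: thresholds.** Solving the same function for 80% power, the lowest UC incidence is 27.9% at RR 2.0, 19.7% at RR 2.5 and 15.8% at RR 3.0. The RR detectable with 80% power is 1.92 at UC 30%, 2.13 at 25%, 2.48 at 20%, 2.97 at 16% and 3.38 at 14%.

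**Step 5: no loss to follow-up.** With all 294/2 = 147 per group followed, RR 2.0 power is 78.7% at UC 25% and 67.2% at UC 20%, still below 80%.

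**The case against.** The strongest reply is that nothing in the conduct of the trial turns on this. At the incidence the protocol cites, power for RR 2.0 is at least 83.5%. That stands: N is not shown to be wrong.

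Second, the sentence names no relative risk and does not define adequate power, and Table 1 covers larger effects. At RR 2.5 or 3.0 the trial does keep 80% power well below 30%. That also stands, so the sentence is overstated rather than false in every case. But RR 2.0 is the only effect named for the chosen N, and the sentence follows directly from it.

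Third, the cited figure is *over* 30% with no point value, so the gap of about 2 points to 27.9% is a minimum. If the intended figure were near 34% (an assumption), the gap would be about 6 points. Neither is much lower.

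Fourth, the planned primary analysis is a GEE over three visits (Section 12.4), and Section 12.2 calls the single-outcome calculation conservative for that reason. The power of the GEE is indeed unknown. The documents give no visit-level rates or within-patient correlation, so an unquantified gain cannot support the statement.

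Finally, 14% vs 7% is a possible misreading, not something the protocol states. It shows why the label is needed; it is not evidence of a wrong design.

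**Conclusion.** The concern holds. Section 12.2 claims a robustness that the design lacks at the effect size used to set N. The arm is inferred from arithmetic, but firmly: 12 of 12 cells fit one reading and none fits the other. All power figures here apply to the protocol's single-binary-outcome calculation with 132 per group.

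Two related points are secondary, and the conclusion does not depend on them.

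- Calling RR 2.0 conservative has no support in the cited RR of 3.8, which compares extraction with no extraction, not device with hand support. The protocol's other uses of the word, for the single-outcome calculation and for 90% retention, have stated reasons.
- The UC incidence is uncertain in both directions. The cited cohort figure is that "the incidence of jaw joint symptoms lasting more than 1 month was 34.3 per 100 person-years", and Section 2.1 describes that study's outcome as "the onset of jaw joint symptoms (i.e., TMJ noise and jaw pain) in individuals who had 3rd molar extractions". The trial counts any qualifying pain report at 1, 3 or 6 months, with no duration requirement and without noise (Section 3.2.1). If the rate were constant (an assumption the documents do not support), 6-month risk would be 1 − exp(−0.343 × 0.5) = 15.8%, where RR 2.0 power is about 51%. The trial's lack of a duration requirement could instead push incidence above 30%.

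**What to change.** Keep N = 294 and change Section 12.2 only:

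1. Label the first column of Table 1 as EC incidence, with UC equal to RR times that value, or add a UC column. State the design assumption as UC 28% vs EC 14%.
2. Replace the sentence on a much lower control incidence with: *With 132 per group, 80% power is kept down to a UC incidence of about 28% at RR 2.0, 20% at RR 2.5 and 16% at RR 3.0.* Follow it with the power grid above, and note that it applies to the single-binary-outcome calculation and not to the GEE.
3. Remove the word *conservative* from the description of RR 2.0 only.
4. Add a sentence saying that the UC incidence may be lower or higher than the cited figure, because the outcome definition and time base differ.

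The cost is one column label, a few sentences and a small table. No patients are added and no analysis changes. The stated power at low control incidence becomes less favourable.

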**Table 1. Sample size per group**

TMD pain incidence	Relative risk		
	2.0	2.5	3.0
14%	132	65	39
20%	81	38	22
25%	58	26	14
30%	42	18	9

## 12.3 Planned Interim Analyses (if applicable)

No interim analyses are planned.

### 12.3.1 Safety Review

If the device becomes loose or excessive force is placed on it during the procedure, there is a potential risk this could compromise the support of the patient's jaw, resulting in jaw injury.

While the proposed intervention does not include changes to practice that may harm patient participants, a special focus will be the safety of patients exposed to the study intervention.

We have no specific outcome measures related to safety but participating surgeons will be required to record all AEs, including SAEs, according to procedures specified in Section 9.2

### 12.3.2 Efficacy Review

Interim analyses are not planned for this clinical trial. However, should it be determined that an interim analysis should occur, the exact sequential monitoring plan must be reviewed and approved by the NIDCR in consultation with the MMOR before any interim formal tests occur. For the repeated tests of efficacy, we will use the group sequential method of Lan and DeMets  for which neither the number of tests nor the increments between tests needs to be pre-specified. The approach requires specification of a so-called alpha spending function, chosen to give a low probability of stopping in the early formal analyses. We will propose the well-known O'Brien-Fleming spending function with total alpha 0.05.

## 12.4 Final Analysis Plan

All analyses will be by intention-to-treat, with participants included in the group (UC or EC) to which they were randomly assigned.

**Primary analysis.** The primary outcome is incidence of TMD pain within a 6-month follow-up period (a binary dependent variable). The incidence of TMD pain post-surgically will be compared between UC and EC groups. This primary TMD outcome is deemed to have occurred if the patient's self report in the *Patient 1-, 3- and 6-month Follow-up Questionnaires* endorses either or both of the following questions: Pain in jaw with wide opening, or pain in temples, jaw joints or jaw muscles. The primary analysis will include all available follow-up measures (1, 3, and 6 months) for each participant to

estimate incident TMD pain. The UC and EC groups will be compared using an analysis that has the form of logistic regression, but which accounts for correlation of visits within participants using generalized estimating equations (GEE) with each participant being a cluster. The analysis will include group (UC vs. EC), which tests whether the two groups differ in overall frequency of TMD pain; time (1, 3, and 6 months, as a categorical factor); and their interaction (i.e., the time-by-group interaction), which tests for different patterns of change over time in frequency of TMD pain.

In the event of noteworthy amounts of missing data (e.g., patients lost to follow-up or questionnaires not completed), we will check the primary analysis by using standard multiple imputation methods, as implemented in the most recent version of the SAS software (SAS Institute Inc., Cary NC, v. 9.4 or higher), to multiply impute missing data and perform tests. Specifically, we will use SAS's FCS method to create 20 "complete" datasets and otherwise use the defaults in SAS's procedures.

**Secondary analysis.** The primary analysis will not include adjusters, as the randomization should balance the groups. As a check on this, an adjusted version of the primary analysis will include adjusters differing substantially between the two randomized groups, selected from the list of potential adjusters given below (see "Potential Adjusters", below).

Other secondary analyses are as follows:

1. The incidence of TMD pain, as measured with the validated *TMD Pain Screener Questionnaire* (*binary dependent variable*), will be compared between the UC and EC groups within a 6-month follow-up period based on patients' self report in the *Patient 1-, 3- and 6-month Follow-up Questionnaire*. These analyses will have the same form as the primary analysis.
2. TMD pain intensity, as measured with the validated Characteristic Pain Intensity (CPI) within a 6-month follow-up period (treated as a continuous measure), will be compared between the UC and EC groups based on patients' self report in the *Patient 1-, 3- and 6-month Follow-up Questionnaire*. Unadjusted and adjusted analyses (using adjusters selected as described above) will be performed using GEE as in the primary analysis.
3. Baseline characteristics, specifically all of the potential adjusters listed below (see "Potential Adjusters", below), will be compared between the UC and EC groups. Analyses will use t-tests, possibly after transforming the measure because it has a skewed distribution, Chi-squared test and Fisher's Exact Test.

4. The UC and EC groups will be compared for TMJ noise, pain characteristics (e.g., location in temple or jaw, and occurrence with wide opening of mouth) and change in jaw pain since it started, within a 6-month follow-up period based on patients' self report in the *Patient 1-, 3- and 6-month Follow-up Questionnaire*. These analyses will have the same form as the primary analysis.
5. A descriptive summary of the experiences of surgeons and dental assistants with the new device at mid-way through recruitment of patients and at the end of recruitment based on their self report in the *Doctor Questionnaire Regarding Use of the Device* and *Dental Assistant Questionnaire Regarding Use of the Device*, respectively,

All analyses will use SAS version 9.4 or later (SAS Institute Inc., Cary, NC). All tests will use a significance threshold of 0.05 (2-tailed).

Potential adjusters: The following characteristics will be compared between the UC and EC groups as potential adjusters:

- Patient demographics
- Baseline patient-reported symptoms (e.g., TMJ noise, pain or discomfort around wisdom teeth, frequency of oral habits as measured with the Oral Behaviors Checklist (OBC), and health status; see *Patient Baseline Questionnaire*).
- Baseline clinical findings by the surgeon (e.g., TMJ noise, eruption status, pericoronitis, soft-tissue infection, reason for extraction, difficulty of extraction, length and duration of the surgery, and pain or discomfort around third molars); see *Doctor Surgery Questionnaire*.
- Procedural characteristics, identified by the surgeon (e.g., type of extraction, amount of bone removal, use of grafting); see *Doctor Surgery Questionnaire*.

